6.4. WINDOWING CONVENTIONS

Not applicable.

6.5. STATISTICAL TESTS

All tests of treatment effects will be conducted at a 2-sided alpha level of 0.05, or with 2-sided 95% CIs.

6.6. COMMON CALCULATIONS

For continuous measurements, change from baseline will be calculated as:

Test Value at scheduled Visit X - Baseline Value

Ratio to baseline will be calculated for pharmacodynamic endpoints as:

Test Value (post baseline) / Baseline Value

6.7. SOFTWARE VERSION

Non-compartmental analysis of PK data for final or any interim analysis, and descriptive statistics and graphics for any interim PK analysis, will be performed using Phoenix WinNonlin® 6.4 or higher (Certara, L.P., Princeton, New Jersey, USA). All other analyses, statistics, and graphics (including PK/PD) will be conducted using Statistical Analysis System (SAS) System® Version 9.4 or higher (SAS-Institute, Cary, North Carolina, USA).

7. STATISTICAL CONSIDERATIONS

7.1. ADJUSTMENTS FOR COVARIATES AND FACTORS TO BE INCLUDED IN ANALYSES

The change from baseline on Day 22 of peripheral eosinophil count will be compared between ANB020 and placebo using a mixed-model repeated measures (MMRM) analysis with treatment, visit of measurement, and treatment by visit interaction as fixed effects and baseline eosinophil count and baseline by visit interaction as a covariate.

7.2. MULTICENTER STUDIES

There are a total 7 centers from United Kingdom (3) and USA (4) included in this study.

Document: \\ieedc-vnasc01\biosdata\AnaptysBio\ANB020\CYA74392\Biostatistics\Documentation\SAP\Final\20181218

Author: Version Number: 1.0
Version Date: 18Dec2018

Template No: CS_TP_BS016 Revision 4 Reference: CS_WI_BS005

Effective Date: 01Apr2016

7.3. MISSING DATA

For non-PK/PD data, no imputations will be performed on missing data. Partial dates will be imputed as per Appendix 1. Missing PK or PD data will be handled as described in Section 19 or Section 20.

7.4. MULTIPLE COMPARISONS/ MULTIPLICITY

Not applicable.

7.5. EXAMINATION OF SUBGROUPS

No subgroups analysis will be performed for this study.

OUTPUT PRESENTATIONS

The templates provided with this SAP describe the presentations for this study and the format and content of the summary tables, figures and listings to be provided by IQVIA Biostatistics.

All visit assessments will be presented according to the nominal visit name.

DISPOSITION AND WITHDRAWALS

All patients who provide informed consent will be accounted for.

Data collected in Early Termination (ET) and End of Study (EOS) pages in the electronic Case Report Form (eCRF) will be used to present disposition and withdrawal results. Frequency table will be provided for:

Number of patients screened per Informed Consent.

Number of patients eligible at screening.

Number of screen failures (from EoS page).

Number of patients in the Randomized Analysis Set (patients who are assigned treatment).

Number of patients randomized at day 1.

Number of patients willing to participate at Day 1.

Number of patients in the Safety Analysis Set (patients administered the treatment).

Document: \\ieedc-vnasc01\biosdata\AnaptysBio\ANB020\CYA74392\Biostatistics\Documentation\SAP\Final\20181218 \\
Author: \text{Version Number: 1.0}

Version Date: 18Dec2018

Template No: CS_TP_BS016 Revision 4 Reference: CS_WI_BS005

Effective Date: 01Apr2016

Clinical Study Report ANB020-004 - Original

AnaptysBio Inc PROTOCOL ANB020-004 Page 21 of 46

Number of patients in the Full Analysis Set.

Number of patients in the Pharmacokinetic Analysis Set.

Number of patients in the Pharmacodynamic Analysis Set.

Number of patients who completed the study (from EoS page).

Number of patients who Completed the Study assessments till Day 36.

Number of patients who discontinued/withdrew the study (from EoT page).

Primary reason for discontinuation (from EoT page).

A listing will be presented with the following details.

screen failure (Yes/No)?

Willing to Participate at Day 1

assigned treatment

completed study (Yes/No)?

If not completed the study, then reason for end of treatment.

10. DEMOGRAPHIC AND OTHER BASELINE CHARACTERISTICS

Demographic data and other baseline characteristics will be presented for the SAF. No statistical testing will be carried out for demographic or other baseline characteristics.

Summary statistics will be provided for:

Age (years) - calculated relative to date of informed consent

Weight (kg) as collected on the Vital Signs Screening eCRF

Height (cm) as collected on the Vital Signs Screening eCRF

BMI (kg/m²) as collected on the Vital Signs Screening eCRF

Frequency tables will be provided for:

Gender

Document: \\ieedc-vnasc01\\biosdata\AnaptysBio\ANB020\CYA74392\\Biostatistics\Documentation\SAP\Final\20181218

Author:

Version Number: 1.0 Version Date: 18Dec2018

Reference: CS_WI_BS005

Template No: CS_TP_BS016 Revision 4

Effective Date: 01Apr2016

AnaptysBio, ANB020 CONFIDENTIAL

IND 126765, SN 0035

Clinical Study Report ANB020-004 - Original

AnaptysBio Inc PROTOCOL ANB020-004 Page 22 of 46

IQVIA STATISTICAL ANALYSIS PLAN

Women of child bearing potential

Race

Ethnicity

A listing for patient demographic data and other baseline characteristics will be presented.

11. PROTOCOL DEVIATIONS

All protocol deviations observed during study conduct will be captured in Clinical Trial Management

System (CTMS).

The Investigator and Sponsor will review the protocol violation records from CTMS and provide

confirmation on the categorization of violations as major/ critical/ minor.

Major protocol deviations or events include changes to the procedures that may impact the quality of

the data or any circumstances that can alter the evaluation of the PK or PD data. Examples include,

but may not be limited to, sample processing errors that lead to inaccurate bioanalytical results,

incomplete dose administered, incomplete PK or PD profile collected, and use of disallowed

concomitant medication thought to affect PK or PD. In the case of a major protocol deviation or event,

the corresponding PK or PD data collected will be excluded from the summaries and statistical analyses,

yet will be reported in the study result listings.

A list of major protocol deviations that could significantly affect study assessments will be provided. The

incidence of each protocol violation will be listed. A frequency table for major protocol violations will be

provided for Safety Analysis Set. Major protocol deviations or events that impact the quality of the PK

and/or PD data will be listed only.

If a patient refuses blood collection for PK analysis, this will not be considered a protocol violation as

the PK analysis is a secondary objective.

12. MEDICAL HISTORY

The frequency and percentage will be provided for medical history findings summarized by system

organ class (SOC), preferred terms (PT) and report term for the SAF. Medical history will be coded

using version 20.0 (or higher) of MedDRA.

Document:

\\ieedc-vnasc01\biosdata\AnaptysBio\ANB020\CYA74392\Biostatistics\Documentation\SAP\Final\20181218

Author:

Version Number: Version Date: 18Dec2018

Reference: CS_WI_BS005

Template No: CS_TP_BS016 Revision 4

Effective Date: 01Apr2016

Clinical Study Report ANB020-004 - Original

AnaptysBio Inc PROTOCOL ANB020-004 Page 23 of 46

STATISTICAL ANALYSIS PLAN

Patients experiencing multiple events within the same SOC will only be counted once within that SOC and multiple PTs within the same SOC will only be counted once for each unique PT within the SOC.

Summary tables will be table sorted in descending order of SOC and descending order of PT within SOC.

Percentages will be sorted by decreasing frequency of SOC and PT within SOC for overall. Events will be mentioned as "Uncoded" if they are not coded yet.

A listing of medical history diagnosis with all details will be presented.

13. CONCOMITANT ILLNESSES

Medical history that are ongoing at the screening will be coded using version 20.0 (or higher) of MedDRA and presented similar to medical history.

The frequency and percentage will be provided summarized by SOC and PT for the SAF.

Patients experiencing multiple events within the same SOC will only be counted once within that SOC and multiple PTs within the same SOC will only be counted once for each unique PT within the SOC.

Percentages will be sorted by decreasing frequency of SOC and PT within SOC for overall. Events will be mentioned as "Uncoded" if they are not coded yet.

A listing of ongoing medical illnesses with all details will be presented along with medical history conditions.

14. CONCOMITANT MEDICATIONS

A frequency table will be provided for prior and concomitant medications and will be summarized by SOC and PT for the SAF. Medications will be coded using WHO drug dictionary version Dec 2016.

Patients with multiple usage of the same medication within the same SOC and PT will only be counted once within that level.

Percentages will be sorted by decreasing frequency of SOC and PT for overall. Medications will be mentioned as "Uncoded" if they are not coded yet.

See Appendix 1 for handling of partial dates for medications. If it is not possible to define a medication as prior or concomitant, the medication will be classified by the worst case; i.e. concomitant.

Document: \\ieedc-vnasc01\biosdata\AnaptysBio\ANB020\CYA74392\Biostatistics\Documentation\SAP\Final\20181218 \\
Author: \quad \qqq \quad \

Version Date: 18Dec2018

Reference: CS_WI_BS005

Template No: CS_TP_BS016 Revision 4

Effective Date: 01Apr2016

Clinical Study Report ANB020-004 - Original

AnaptysBio Inc PROTOCOL ANB020-004 Page 24 of 46

'Prior' medications are medications which started and stopped prior to the administration of study drug.

'Concomitant' medications are medications which:

started prior to, on or after the administration of study drug,

AND ended on or after the date of administration of study drug or were ongoing at the end of the study.

A listing for medication with all details will be presented for the SAF.

15. STUDY TREATMENT EXPOSURE

A listing of study drug exposure will be presented, with details of start date & time and end date & time of infusion and total volume administered as well as reason if <100 ml was infused. Data from IP Administration eCRF page will be used to generate the summary table and listing.

16. STUDY TREATMENT COMPLIANCE

Overall compliance is expected as the study treatment is being administered at the clinic, however no summary will be provided for compliance.

17. EFFICACY OUTCOMES

17.1. PRIMARY ENDPOINTS

17.1.1.PRIMARY EFFICACY ENDPOINT

Not applicable.

17.1.2. PRIMARY PHARMACODYNAMIC ENDPOINT

Reduction of peripheral eosinophil count from Baseline (Day 1) to Day 22

17.1.2.1. Analysis of Primary Pharmacodynamic Endpoint

Pharmacodynamic analysis will be carried out for the PD Analysis Set. For analysis of primary PD endpoint, refer to Section 20 for details.

Document: \\ieedc-vnasc01\biosdata\AnaptysBio\ANB020\CYA74392\Biostatistics\Documentation\SAP\Final\20181218

Author: Version Number: 1.0
Version Date: 18Dec2018

Template No: CS_TP_BS016 Revision 4 Reference: CS_WI_BS005

Effective Date: 01Apr2016

AnaptysBio Inc PROTOCOL ANB020-004 Page 25 of 46

17.2. SECONDARY ENDPOINTS

17.2.1.SECONDARY EFFICACY ENDPOINTS

Change in FEV₁ (Litres) from Baseline (Day 1) to the EOS visit (Day 127)

Change in FeNO (ppb) from Baseline (Day 1) to the EOS visit (Day 127)

17.2.1.1. Analysis of Secondary Efficacy Endpoints

The null hypothesis for the secondary efficacy analysis is:

H0: There is no difference in change from baseline on day 127 (for FEV₁ and FeNO) between ANB020 and placebo.

Vs the alternative:

H1: There is a difference in change from baseline on day 127 (for FEV₁ and FeNO) between ANB020 and placebo.

The analysis of the secondary efficacy endpoints will be carried out for the FAS population.

Day1 pre-bronchodilator spirometry assessment will be considered as the baseline.

The actual and change from baseline (Day 1) to the EOS visit (Day 127) for FEV1 and FeNO will be summarized using descriptive statistics by treatment groups at all time points where assessment is done. Change from baseline will be evaluated where possible.

Change from baseline for FEV₁ and FeNO will be compared between ANB020 and placebo using an analysis of covariance (ANCOVA) with treatment as fixed effect and baseline result as covariate and patient as a random effect. An unstructured covariance matrix will be used. If the model fails to converge, then an appropriate covariance matrix [e.g. compound symmetric (CS), CHS, AR] will be selected based on the Akaike Information Criteria (AIC). For AIC, a lower value will imply a better fit.

The following statistics will be presented:

Treatment Least Square Mean (LSM)

Treatment LSM difference

Standard error of treatment LSM difference

95% confidence interval (CI)

Document: \\ieedc-vnasc01\biosdata\AnaptysBio\ANB020\CYA74392\Biostatistics\Documentation\SAP\Final\20181218 \\
Author: \text{Version Number: 1.0}

Version Date: 18Dec2018

Template No: CS_TP_BS016 Revision 4 Reference: CS_WI_BS005

Effective Date: 01Apr2016

Clinical Study Report ANB020-004 - Original

AnaptysBio Inc PROTOCOL ANB020-004 Page 26 of 46

IQVIA STATISTICAL ANALYSIS PLAN

P-value for the difference

A supportive analyses will be performed using an MMRM analysis. The model includes terms for treatment, time point of measurement, and treatment by time point interaction as fixed effects and baseline value and baseline*time point as covariate. At each visit day, model-based LSMs for the treatment effects, 95% CIs, and p-values will be calculated for within and between treatment comparisons.

Patient-wise data listings will be provided.

17.2.2.SECONDARY PHARMACOKINETIC ENDPOINTS

Maximum observed concentration (C_{max})

Time to maximum observed concentration (t_{max})

Area under the concentration-time curve in serum from time zero (pre-dose) extrapolated to infinite time $[AUC_{(0-inf)}]$

Area under the serum concentration-time curve from time zero to the time of the last quantifiable concentration [AUC_(0-last)]

Systemic clearance (CL)

Apparent terminal rate constant (λ_z)

Apparent terminal half-life (t_{1/2})

Volume of distribution during terminal phase (Vz)

Volume of distribution at steady state following intravenous dosing (V_{SS})

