## **9.5 Efficacy analysis**

The secondary efficacy variables (change in FEV1 and change in FeNO), and exploratory variables (change in clinical scores for ACQ, PGIC, and CGIC, and applicable diary assessments) will be analyzed using the full analysis set.

For secondary efficacy endpoint, actual and change in FEV1 from Baseline (Day 1) to the EOS visit (Day 127) will be summarized using descriptive statistics. Change from Baseline will be compared between ANB020 and placebo using a mixed-effect analysis of covariance (ANCOVA). This model includes, fixed effect as treatment, baseline efficacy variable levels as covariates, and patient as a random effect. Appropriate covariance structure will be used. Treatment differences will be presented with corresponding p-values for the test of no difference and 95% CI.

Supportive analyses will be performed using a mixed-model repeated measures (MMRM) analysis. The model includes terms for treatment, time point of measurement, and treatment by time point interaction as fixed effects and Baseline value (pre-dose measurement at randomization [Day 1]) as covariate. At each visit day, ANB020 will be compared with placebo and model-based least squares means for the treatment effects, 95% CIs, and p-values will be calculated for within and between treatment comparisons.

Other secondary efficacy endpoint and applicable exploratory endpoints analyses will be performed same as FEV1 analyses.

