Table 14 2 1 2 Secondary Efficacy Endpoint: Change in FEV1 (Litres) from Baseline to Day 127 – Full Analysis Set

	ANB020	Placebo
Statistic	(N=XX)	(N=XX)
n e e e e e e e e e e e e e e e e e e e	XX	XX
LS Mean	XXX.XX	XXX.XX
SE of LS Mean	XX.XXX	XX.XXX
95% CI	[XXX.XX, XXX.XX]	[xxx.xx, xxx.xx]
LS Mean Difference (ANB020 – Placebo)	XX.XX	
SE of LS Mean Difference	XX.XX	
95% CI for LS Mean Difference	[xx.xx, xx.xx]	
P-value	X.XXXX	

Source: Listing 16.2.6.2

Note:

- LS: Least Squares; SE: Standard Error; CI: Confidence Interval;
- n is the number of subjects with non-missing values
- N is the number of subjects within each treatment group under Full Analysis Set
- P-value is obtained using mixed-effect ANCOVA model with treatment as fixed effect and baseline result as covariate and patient as a random effect

- Similar table will be generated for FeNO as following:

Table 14 2 2 1

Fractional Exhaled Nitric Oxide (FeNO) (in ppb) Test – Full Analysis Set

Source listing for Table 14.2.1 is 16.2.6.1

Table 14 2 2 2

Secondary Efficacy Endpoint: Change in Fractional Exhaled Nitric Oxide(FeNO) (in ppb) from Baseline to Day 127 - Full Analysis Set

Table 14 2 1 3

Secondary Efficacy Endpoint: Change in FEV1 (Litres) from Baseline - Supportive Analysis - Full Analysis Set

Document: \\ieedc-vnasc01\biosdata\\AnaptysBio\ANB020\CYA74392\Biostatistics\Documentation\SAP\Final\20181218

Author: Version Number: 1.0

Version Date: 18Dec2018

CONFIDENTIAL

Table Shells

Clinical Study Report ANB020-004 - Original

AnaptysBio Inc. PROTOCOL ANB020-004 Page 25 of 51

		ANB020	Placebo
sit	Statistic	(N=XX)	(N=XX)
ay 2	n	xx	xx
-, -	LS Mean	XXX.XX	XXX.XX
	SE of LS Mean	XX.XXX	XX.XXX
	95% CI	[xxx.xx, xxx.xx]	[xxx.xx, xxx.xx]
	LS Mean Difference (ANB020 – Placebo)	XX.XX	• • •
	SE of LS Mean Difference	XX.XX	
	95% CI for LS Mean Difference	[xx.xx, xx.xx]	
	P-value	x.xxxx	
ay 8	n	xx	xx
	LS Mean	XXX.XX	XXX.XX
	SE of LS Mean	XX.XXX	XX.XXX
	95% CI	[xxx.xx, xxx.xx]	[xxx.xx, xxx.xx]
	LS Mean Difference (ANB020 – Placebo)	XX.XX	• • •
	SE of LS Mean Difference	XX.XX	
	95% CI for LS Mean Difference	[xx.xx, xx.xx]	
	P-value	X.XXXX	
TC]			

Source: Listing 16.2.6.2

Note:

- LS: Least Squares; SE: Standard Error; CI: Confidence Interval; MMRM: Mixed Model for Repeated Measures;
- n is the number of subjects with non-missing values
- N is the number of subjects within each treatment group under Full Analysis Set

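### FEV1 and FeNO at Day 127: the ANCOVA text, the sample code and the table shell do not describe the same analysis

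*SAP*

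**What the plan says.** - **Endpoint and hypothesis.** SAP 17.2.1 defines the change in FEV1 and in FeNO "from Baseline (Day 1) to the EOS visit (Day 127"). The null hypothesis in SAP 17.2.1.1 is "There is no difference in change from baseline on day 127" between the arms.
- **Model.** SAP 17.2.1.1 compares the arms "using an analysis of covariance (ANCOVA) with treatment as fixed effect and baseline result as covariate and patient as a random effect". It starts from an unstructured covariance matrix and continues: "If the model fails to converge, then an appropriate covariance matrix" (CS, CHS or AR are the examples) is chosen by AIC. Protocol 9.5 has the same random term: "This model includes, fixed effect as treatment, baseline efficacy variable levels as covariates, and patient as a random effect".
- **Shells.** Shell 14.2.1.2 (FEV1) is titled for the change to Day 127 and has one n per arm, where "n is the number of subjects with non-missing values". Its contrast row is "LS Mean Difference (ANB020 – Placebo"). Shell 14.2.2.2 repeats it for FeNO. The repeated-measures results have their own by-visit shell, 14.2.1.3: "Secondary Efficacy Endpoint: Change in FEV1 (Litres) from Baseline - Supportive Analysis - Full Analysis Set". The footnote with a random patient effect also appears under ACQ (14.2.3.2) and IgE (14.2.6.1).
- **Sample code.** The ANCOVA block in SAP Appendix 3 models change on `trt` and `base`, with no WHERE, no BY and no visit term. It has `Random trt / subject=usubjid type=UN`, an LSMEANS line without a difference option, and the contrast `trt -1 1`.

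**The concern.** The hypothesis and the main shells call for one Day 127 value per patient. A random patient effect and a choice among covariance structures make sense only with repeated records per patient. A programmer could therefore drop the surplus terms, fit them to data that cannot identify them, or take them as a sign that all visits belong in the model.

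The sample code does not settle this, because nothing in it selects Day 127. If it were run on all visits, a table titled for Day 127 would hold an average over follow-up, which no hypothesis or title asks for. Separately, the contrast line could print the treatment difference and its confidence limits with the wrong sign.

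**Working it through.** The plan gives no power, SD or effect size for these endpoints (SAP Section 3 says the sample size is not based on power), so there is no figure to reproduce. The check is of structure.

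**Inputs.** About 24 patients, 1:1, so 12 per arm (SAP Section 3). Post-baseline clinic visits are Days 2, 8, 22, 36, 64, 85, 106 and 127, so eight; ACQ omits Day 2, so seven (SAP Section 3). The treatment codings printed are ANB020/Placebo (CMH code, Appendix 3) and Dummy1/Dummy2 and 1/2 (Appendix 2).

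**1. One record per patient, text model.** The variance of a record is τ² + σ² (patient plus residual). Only the sum enters the likelihood, so 1 of 2 parameters is identifiable. On a generated set of 12 per arm, giving the patient effect 0, 25, 50, 75 or 95% of the variance left the REML log-likelihood at −16.1094 and the arm difference at 0.926 throughout. The model is ordinary ANCOVA, with 24 − 3 = 21 residual degrees of freedom if all 24 patients have data.

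**2. One record per patient, sample RANDOM line.** The parameters are g11, g12, g22 and σ². An ANB020 record has variance g11 + σ² and a placebo record g22 + σ². No patient receives both treatments, so g12 never appears, and 2 of 4 parameters are identifiable. The line amounts to a separate variance for each arm, which the text does not plan. In 3000 generated trials (12 per arm, equal true variances, baseline slope −0.3, residual SD 1; Satterthwaite degrees of freedom standing in for the Kenward-Roger option in the code), it changed the 95% CI half-width by a median of +0.1% (5th to 95th percentile −0.7% to +2.1%). It moved the estimate by a median of 0.014 SE (95th percentile 0.14 SE).

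**3. Sample code on all visits.** The covariance of a patient's eight records is g·J + σ²·I, where g is that arm's patient variance, J is all ones and I is the identity. Now 3 of 4 parameters are identifiable. Treatment and baseline are constant within a patient, and this matrix weights complete records equally. The treatment coefficient is therefore the difference in eight-visit means: Day 127 has weight 1/8 = 12.5%, or 1/7 = 14.3% for ACQ. That equals the Day 127 effect only if the effect averages to the same value over the visits.

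The size of the gap needs an assumed profile. Suppose a full effect through Day 85, a fraction r of it left on Day 127, and Day 106 midway. Then average ÷ Day 127 effect = (6 + (1 + r)/2 + r) / (8r) = (6.5 + 1.5r)/(8r):

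| r | ratio |
|---|---|
| 1 | 8/8 = 1.00 |
| 0.75 | 7.625/6 = 1.27 |
| 0.5 | 7.25/4 = 1.81 |
| 0.25 | 6.875/2 = 3.44 |

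The range shows only that the answer depends on r, which the documents do not give.

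**4. Sign.** All three printed codings sort ANB020 first. Under default class order `trt -1 1` is then −ANB020 + Placebo. On the generated set in step 1 it returned −0.926, where the shell quantity is +0.926. The two-sided p-value is the same.

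**5. Which Day 127 record.** Protocol 6.1.2 plans pre- and post-bronchodilator spirometry at all clinic visits, while the note to Listing 16.2.6.2 says post-bronchodilator readings are captured only on Day 1. SAP 17.2.1.1 names the pre-bronchodilator value for baseline but not for Day 127. Appendix 2 stores EOS and early termination as one visit, and SAP 6.4 has no windowing, so a visit filter alone would also admit early-termination records. The FEV1, FeNO and ACQ shells are titled Day 127; the IgE shell is titled Day 127/ET.

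**The case against.** **The code is only a sample.** It has a placeholder data set, and a Day 127 subset could be made upstream. The endpoint, hypothesis, shell title, single n per arm and separate by-visit shell all point to one record. This stands: an all-visits run would go against the rest of the SAP, and a missing WHERE line is weak evidence of intent. But no text states the subset, and the covariance wording points the other way.

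**The random term does no harm.** With one record this is right; steps 1 and 2 show almost no change.

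**The supportive MMRM covers Day 127.** It does give a between-arm contrast at each visit, which limits the damage. It remains the supportive analysis.

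**The class order is not stated.** True. The garbled Cox code mentions placebo first, and that order would restore the sign. The shell prints both LS means beside the difference, so a reversal could be noticed.

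**A stronger reading.** A reader might infer that the average would overstate the Day 127 effect, since Protocol 2.1 gives a half-life of about 14 to 17 days and Day 127 is 126/17 = 7.4 to 126/14 = 9.0 half-lives after the single dose. The documents do not establish this. Inhibition was seen through 84 days because that was the last time point observed, not because it then faded. It was also an ex vivo IFN-γ measure in healthy subjects, not FEV1 or FeNO in patients.

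**Conclusion.** The mismatch is real, and its expected consequence is small. On the one-record reading, the random effect and the UN/CS/CHS/AR choices are surplus: the text model is ordinary ANCOVA, and the sample RANDOM line only adds arm-specific variances, with a median CI change of about 0.1% under equal true variances.

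The part that could matter depends on how the code is run. Unfiltered, it targets an eight-visit average with 12.5% weight on Day 127 when data are complete. The size and direction of the gap from the Day 127 effect are unknown. With default class order, the printed difference and its limits would have the opposite sign to the shell, with the p-value unchanged.

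A reader might also infer that the planned FEV1 and FeNO results are invalid, or that error rates are inflated. The documents do not support that: the text model applied to one record per patient gives a sound estimate, and they supply no profile, SD or correlation from which to compute an error rate. Severity is minor to should-fix: two secondary endpoints and, through the shared footnote, exploratory ACQ and IgE, in an unpowered study of about 24 patients.

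**What to change.** - **SAP 17.2.1.1.** State that the ANCOVA uses one Day 127 change per patient, with treatment and baseline only. For FEV1 name the pre-bronchodilator value, matching the stated baseline. Say whether early-termination records stored under EOS/ET are included, consistently with each shell title (Day 127 for FEV1, FeNO and ACQ; Day 127/ET for IgE). Delete the random patient effect, the unstructured matrix and the CS/CHS/AR fallback.
- **SAP Appendix 3.** Delete the RANDOM line, add the visit filter, and write the contrast as ANB020 minus Placebo with the class order stated.
- **Shells.** Align the footnotes of 14.2.1.2, 14.2.2.2, 14.2.3.2 and 14.2.6.1.
- **SAP 3.2.** Record the change, after checking the efficacy section of Protocol Amendment 4, which the SAP cites and which was not available here. Protocol 9.0 allows method changes to be documented in the SAP.

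The cost is a few lines of text, one code block, four footnotes and one entry in SAP 3.2. No new data are needed.

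Two items are separate clean-up and not part of this point: the cytokine shell 14.4.2.3.2 carries the ANCOVA footnote although SAP Section 20 plans an MMRM, and the MMRM sample code has `base*trt` where SAP 17.2.1.1 specifies baseline by time point.
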